The methodology described in detail in field number 14 is summarized. The four premolars due to be extracted for orthodontic reasons will have at least a 1 x 1 millimeter surface flattened with a 169L bur. That surface will be polished with fine and extra fine sandpaper discs. This will improve the evaluation in the dental laboratory, especially of Vickers hardness. A maxillary premolar will be whitened at home with Opalescence 10% CP with PF in 30 sets of subjects and in 10 sets with Opalescence 10% CP without PF for 14 nights. The opposite maxillary premolar will be used as a control (no treatment). The mandibular and collateral premolar of the one that was whitened At-Home it will be whitened in all 40 sets at the office with Opalescent Boost PF 40% HP for a total of 60 minutes (three consecutive times of 20 minutes each). The opposite mandibular premolar to the control in three of the 30 sets of premolars that were treated with PF and in three of the 10 sets of premolars that were bleached without PF will have two narrow bands of Block-Out resin placed on a premolar. The area between the bands will be etched for 15 seconds with Ultra-Etch, a 35% phosphoric acid on the day of the extraction appointment. The extractions will be accomplished 14 days after finishing the whitening At-Home and In-Office procedures. The collected samples will be delivered to TTI for evaluation.

The *in-vivo* treatment of the teeth and the extractions will be performed at UIC. Treatment effects will be evaluated at TTI in Zionsville, Indiana, USA.

7- Keywords:

Demineralization, Teeth whitening, Profilometer, Scanning electron microscope (SEM), Vickers hardness, *in-vivo*.

8- INTRODUCTION OF THE PROJECT:

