Some teeth whitening agents are acidic, and pH values below 5.5 have been shown to cause demineralization of tooth structure. This may be a reason some studies have shown that a loss of microhardness occurs when using some acidic tooth-whitening products. In a study by Attin et al. 2009, when samples were kept in a “non-demineralizing solution”, 47% of studies showed no reduction in sample microhardness; when they were kept on “artificial saliva,” 46% of studies showed no reduction; when kept in “human saliva,” 78% of studies showed no reduction. However, after post-treatment, 100% of studies showed no reduction in microhardness when samples were kept in “human saliva.” When studies were conducted “fluoride-free” and microhardness measurements were accomplished, 46% showed no reduction in microhardness; when “fluoride” was used as part of the conditions of the study, 86% of the studies showed no reduction in microhardness. When the study design was *in-vitro*, 48% of the studies showed no reduction in the microhardness; when the study design was *in-situ/in-vivo*, 64% showed no reduction in microhardness. When whitening agents have a neutral pH and enamel samples are maintained in human saliva, there is no loss of hardness or changes in the enamel surface, according to a systematic review and meta-analysis accomplished in New Zealand. (Zanolla J. et al. Influence of tooth whitening on the microhardness of tooth enamel: a systematic review and meta-analysis. Aust Dent Jour 62:276-282;2017).

14- PROJECT METHODOLOGY:

Methods and materials

This study consists of 40 patients requiring the extraction of four permanent first or second premolars for orthodontic reasons. Patients will be recruited from the Universidad Intercontinental (UIC) Graduate Program in Orthodontics, the Universidad Autonoma de Mexico (UNAM) Graduate Program in Orthodontics, and private orthodontist dental offices in the city of Mexico. Patients who identify as needing extraction of the four first or second permanent premolars and who meet the following inclusion criteria will be invited to participate in the study.

Inclusion criteria:

- Have the four premolars in different quadrants that their orthodontist recommends be extracted.
- The premolars to be extracted should have prominent facial surfaces.
- Willing to have the four premolars slightly flattened and smoothed.
- Willing to have all four premolars extracted for orthodontic reasons.
- Between 12 and 35 years of age.

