At the first appointment (selection appointment), the absence of evident cavities or restorations in the four premolars will be clinically verified with an intraoral mirror. Root formation will be confirmed with the panoramic radiograph from the patient's orthodontic chart. The treatment will be explained, and the patient will be allowed to ask questions and discuss any concerns. Subjects will be informed that the study will consist of 4 appointments. If the patient qualifies and agrees to be part of the study, they will be asked to sign an approved Consent Form. Parents or guardians will be asked to sign the consent form for patients under 18 years of age. They will be given a copy of the signed Consent Form. The requirements are that the four teeth that will be extracted for orthodontic reasons will be flattened and polished to produce a one-by-one millimeter surface on the facial or most prominent surface. This will be done with a finishing carbide bur and fine and extra-fine sandpaper discs. Additionally, they must agree to use a whitening tray every night for 14 nights with Opalescence 10% CP with or without PF (potassium nitrate and fluoride) on an upper right premolar (UR) or on the upper left premolar (UL) (the tooth that has the best alignment). The contralateral lower right (LR) or lower left (LL) premolar will be treated with 40% hydrogen peroxide (HP) Opalescence Boost PF at the dental clinic for three 20minute periods according to the manufacturer's instructions**. Thirty of the 40 subjects will treat their UR or UL premolar treated with Opalescence 10% CP with PF. The remaining 10 subjects will treat the UR or UL premolar, with Opalescence 10% CP without PF.

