Title:

Clinical Evaluation of Enamel Microhardness Using At-Home and In-Office Tooth Whitening Agents

NCT#

07165366

Statistical Analysis:

April 21. 2024

Statistical Analysis

Microhardness was summarized for each active treatment group and for the negative and positive controls. Microhardness comparisons for the treatments and negative controls were performed using ANOVA, with a fixed effect for treatment and a random effect to account for within-subject correlations. Pair-wise tests between treatments were performed using the Sidak method to control the overall significance level. Shade change was summarized by treatment and compared between treatments using Wilcoxon Signed Rank tests (at-home versus in-office) and Wilcoxon Rank Sum tests (at-home with versus without PF). A two-sided overall 5% significance level was used.

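### The at-home agent goes to the better-aligned upper premolar and its opposite is the untreated control, so agent and alignment coincide; how subjects come to receive PF or no PF is not stated either

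*Protocol*

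**What the plan says.** **Side.** At the first appointment (Protocol, section 14) the subject agrees to use the tray "on an upper right premolar (UR) or on the upper left premolar (UL) (the tooth that has the best alignment"). Section 6 fixes the comparator: "The opposite maxillary premolar will be used as a control (no treatment"). Elsewhere the Protocol speaks only of a maxillary premolar, or of the UR or UL premolar, and nothing contradicts the alignment rule.

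**PF.** Thirty subjects receive the at-home gel with PF. For the others, section 14 says: "The remaining 10 subjects will treat the UR or UL premolar, with Opalescence 10% CP without PF". Sections 6 and 14 repeat the 30/10 split, but no section says how a subject enters either group. Recruitment is from two university programmes "and private orthodontist dental offices in the city of Mexico", and section 17 has subjects treated in batches of 5 to 10.

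**Analysis.** The SAP describes a model "with a fixed effect for treatment and a random effect to account for within-subject correlations", and names no other term. Shade change with versus without PF is compared by a rank-sum test.

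**The concern.** A split-mouth comparison removes whatever the two teeth share. It does not remove a systematic difference between them, and here the selection rule builds one in: the treated upper tooth is the better-aligned one and the control the less well-aligned one. If alignment, or something that goes with it, affects measured hardness, that effect is added to the treatment effect. It could create a false difference or hide a real loss. The second matters as much as the first, because section 15 of the Protocol expects no change.

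The analysis cannot undo this. No pre-treatment hardness is described, and the model has only treatment and a within-subject random effect. An alignment term would help little, because in the upper arch alignment nearly coincides with treatment.

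The PF question (Protocol, sections 10 and 12) raises a lesser issue. It compares different subjects, so its credibility depends on how they were assigned, and the documents do not say.

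**Working it through.** The documents give no hardness SD, alignment effect or number of comparisons, so there is no figure to reproduce. What follows is an illustration under stated assumptions.

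**Inputs from the documents:** 40 subjects, 30 with PF and 10 without; two-sided overall 5% level with Sidak adjustment (SAP).

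**Assumptions:** four conditions (control, at-home PF, at-home no PF, in-office), hence six pairwise comparisons; alignment alone shifts the treated-minus-control difference by δ = 0.1, 0.2 or 0.3 SD of that difference; no true treatment effect.

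1. Level per comparison: 1 − 0.95^(1/6) = 0.00851, or 0.85%.

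2. Paired t-test, PF versus upper control, n = 30, 29 df, noncentrality δ√30:
   - δ = 0.1: 0.548, rejection 1.80%
   - δ = 0.2: 1.095, rejection 5.50%
   - δ = 0.3: 1.643, rejection 13.92%

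3. A model of the SAP's type: upper control, at-home and in-office tooth in each of 40 subjects, equal correlation ρ between teeth, 120 − 40 − 3 = 77 df, generalised least squares. The whole shift passes into the PF-minus-control estimate. At ρ = 0.5 rejection is 1.99%, 6.53% and 17.03%. At δ = 0.3 it is 17.33% for ρ = 0.3 and 16.80% for ρ = 0.7. The rates exceed those in step 2 because the other teeth and subjects add precision and degrees of freedom without removing the shift.

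4. Sensitivity of step 2 to the number of comparisons: with three (1.70% each) the rates are 3.28%, 8.96% and 20.49%; with ten (0.51% each) they are 1.15%, 3.79% and 10.30%.

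5. With the treated side drawn at random, the alignment shift has random sign across subjects and averages to zero. Simulated rejection (400,000 trials, paired test, n = 30) is 0.83–0.87%, about nominal.

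6. PF versus no PF, microhardness. Suppose all teeth of no-PF subjects carry a common additive shift of 1. With three teeth per subject, the model predicts the at-home tooth from the other two with weight ρ/(1+ρ) each. The share left in the PF contrast is 1 − 2ρ/(1+ρ) = (1−ρ)/(1+ρ):
   - ρ = 0.3: 0.7/1.3 = 54%
   - ρ = 0.5: 0.5/1.5 = 33%
   - ρ = 0.7: 0.3/1.7 = 18%

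   If the 34 unetched lower control teeth (40 − 6) are also counted as controls, the shares are 46%, 27% and 14%.

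7. PF versus no PF, shade change. The rank-sum test has no other tooth to borrow from, so a shift in shade response between the groups would carry through in full.

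**The case against.** The strongest reply is that confounding biases the contrast only if alignment bears on Vickers hardness, and nothing in the documents says that it does. The text also narrows the obvious routes. Inclusion requires that "The premolars to be extracted should have prominent facial surfaces". All four teeth are flattened and polished, to produce "a one-by-one millimeter surface on the facial or most prominent surface". Teeth with restorations or visible cavities are excluded, and no orthodontic movement of these premolars is allowed. Both teeth share saliva, diet, brushing and age. Choosing the better-aligned tooth may also help a single-reservoir tray to fit, although the Protocol gives no such reason. All of this stands, and it limits the point to a risk. It does not show that the risk is absent.

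It also stands that the rejection rates only show what would follow if a shift existed, and that at 0.1 SD the effect is small.

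A reader might infer three stronger things that the documents do not support:

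- **That control teeth were tested on a different surface.** The lingual exception in section 14 describes the resin veneer for the tray tooth. It does not show that controls are prepared differently.
- **That PF was given selectively, or that no-PF subjects cluster by referral source or date.** The documents are silent on method. Silence is not evidence of selection, and the batches of 5 to 10 are scheduling.
- **That different starting shades in the two PF groups would bias the shade test.** The SAP analyses change, so a baseline difference largely cancels; only a difference in response would carry through.

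In the other direction, the random effect in the SAP is a model term, and the random choice in section 17 concerns only the six etched subjects. Neither randomises side or PF. The Protocol does not claim that it randomises either.

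**Conclusion.** The point holds as a design weakness. Apart from ties, the at-home versus upper-control contrast cannot be separated from alignment by anything in the Protocol or SAP. It would be wrong to say that the microhardness result is biased: size and direction are unknown, and no link between alignment and hardness is documented. Under assumed shifts of 0.1, 0.2 and 0.3 SD and six Sidak comparisons, false rejection for PF versus upper control is about 2%, 6% and 14–17%, against 0.85%.

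The PF part is secondary. With no stated method, the 30 versus 10 comparison cannot be read as randomised. For microhardness, the subject's other teeth remove part of any additive subject-level shift, leaving 54/33/18% (46/27/14% with lower controls counted) at assumed correlations of 0.3/0.5/0.7.

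The change is worth making because it is cheap and removes the question. Confidence is medium: the structure is certain, its consequence is not.

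**What to change.** - **Side.** Once both upper premolars are judged able to take the tray, draw the treated side from a concealed random list before the reservoir is built. If only one can take it, flag the side as non-random and omit that subject in a sensitivity analysis.
- **PF.** Draw PF/no PF 3:1 from a concealed list before gel is dispensed. Ten permuted blocks of 4 give exactly 30 and 10.
- **Records.** Record the side and the tested surface of each tooth.
- **If assignment has already happened.** Report the side as chosen by alignment, report how PF was assigned, and describe both comparisons as non-randomised.

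The cost is one concealed list for each draw, a few sentences in the Protocol and SAP, and two recorded items per tooth, with no new visits. The downside is that some trays go on the less well-aligned tooth and may fit less easily, and a few subjects may need a non-random side.

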The null hypothesis is that there will be no change in enamel microhardness when treatment is performed with the whitening agents used in this *in-vivo* study and no changes in enamel characteristics when using potassium nitrate. An alternative hypothesis is that there will be a significant loss of microhardness and in the physical characteristics of the treated premolars, *invivo*.

11- MAIN OBJECTIVE:

The main objective of this study is to determine if there are changes in the microhardness of the enamel surfaces when treating 40 sets of premolars with tooth-whitening agents in an *in-vivo* designed study of premolar teeth treated and extracted from orthodontic patients at UIC.

12- SECONDARY OBJECTIVES:

The secondary objective is to see what changes in enamel surfaces occur with profilometric analysis, and SEM analysis in the premolars submitted to and analyzed at TTI. Potassium nitrate and fluoride are added to tooth-whitening agents as preventive measures to decrease sensitivity and strengthen the enamel. With questionnaires and microhardness measurements, we will be able to determine if agents containing PF are effective and cause physical changes in enamel surfaces.

13- THEORETICAL BASIS:

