A digital scan impression (Dentsply Sirona Scanner) of each subject's dentition will be taken. Study models will be fabricated. On the UR or UL premolar of the model, a 0.5 mm thick veneer of unfilled Block-Out Resin (Ultradent Products Inc.) will be placed. The veneer will be applied on the facial surface or, by exception, on the lingual surface (the most prominent) of the tooth at 1.0 mm mesial, distal, and incisal, and 1.5 mm from the gingival margin. The resin veneer will be lightcured for 15 seconds using a standard visible curing light unit. Bleaching trays will be fabricated from 0.035-inch plastic sheets (Sof-Tray; Ultradent Products Inc.) on each subject's digital model and appropriately trimmed in the UIC laboratory and/or in a private practice laboratory. The trays will be trimmed with micro scissors, 0.5 mm from the gingival margin. Excess tray material will be cut off, and the tray will be carefully removed from the digital model. To reduce gingival trauma, the trays will be trimmed with micro scissors 0.5 mm from the gingival margin. If the patient has started the placement of braces and/or orthodontic bands, the trays will be modified with "windows" to accommodate the brackets, if necessary, and the tray material

over the second molars will be removed to allow a better adaptation (no movements or orthodontic treatments will be allowed in any of the four premolars to be extracted).

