The third appointment will occur on day 15. The subject will return the maxillary whitening tray and will be encouraged to report any concerns with the bleaching treatment or tray usage. During this appointment, the LR or LL premolar and collateral to the one that was bleached at-home will be isolated with OpalDam (Ultradent Products, Inc.) and will be treated with Opalescence Boost PF 40%. The treatment will consist of the application of the gel three separate times, each will remain on the one premolar for 20 minutes, according to the manufacturer's instructions*. If the soft tissue or tooth is sensitive, a soothing gel will be applied to relieve discomfort (Opalescence UltraEZ). Tissue sensitivity usually lasts about thirty minutes and tooth sensitivity usually decreases in two or three days. This appointment will last approximately 90 minutes. During this appointment, an orthodontic separator band or elastic band of 2.5 to 4.5 oz / $\frac{1}{8}$ " to $\frac{1}{4}$ " (depending on interproximal access) will be placed in the gingival area of each premolar to create bone resorption and facilitate an atraumatic extraction. The final color will be taken of the premolar that received 14 days of whitening at-home, as well as the initial and final color of the premolar that will be bleached in-office with VITA Bleachedguide 3-D Master (VITA, Zahnfabrik, Germany); this is to corroborate and document that the teeth were successfully whitened. At this appointment, the subject will be reminded to complete the blood tests required by the UIC oral surgery department since, without these lab tests, the extractions cannot be performed. Therefore, the compensation would not be completed. Also, the subject will be reminded to

continue documenting on the log the brushing at least twice a day for at least one minute each time and will be asked to follow these instructions for the next 14 days.

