On day 29, 14 days after the at-home whitening treatment was ended and 14 days after the inoffice whitening treatment was accomplished, the subject will return to the UIC oral surgery clinic. Six randomly chosen subjects will have two strips of Block-Out Resin placed on one of their "Control" premolars and the tooth will be etched with 35% phosphoric acid for 15 seconds. On that day, all subjects will return to the clinic, where the maxillofacial surgeon(s) will extract the four premolars that the orthodontist prescribed on all subjects.

The implementation program will be performed on 40 subjects between August and December 2024 in blocks of 5 to 10 subjects at a time.

18- RESEARCH SUSPENSION CRITERIA:

If the subjects decide to withdraw from the research study at any time during the study or develop very uncomfortable tooth sensitivity and decide to stop the study, they may do so without any adverse consequences. However, the subject will not receive the compensation previously

stipulated directly with the administrative department of the UIC's School of Dentistry. Until the final protocol is accepted and authorized by Ultradent, this research study may be suspended in its entirety, or the methodology and/or the number of subjects required may be modified. Any modification of this protocol after it has been approved will be cleared with, and an amendment submitted to, the Bioethics Committee of UIC.

19- Explain the Responsibilities of the researcher, the institution, and the funders:

The investigator must verify that the subject meets the Inclusion and Exclusion Criteria to enter the study. The UIC Department of Orthodontics or other referral entity is responsible for identifying patients who may qualify for the research study by identifying one premolar in each of the four quadrants that require extraction due to relief of crowding to allow orthodontic treatment to continue. The sponsor is responsible for funding all necessary materials used to perform the tooth whitening procedures by the subjects, to conduct the research, and accomplish any follow-up treatment required due to the whitening agents.

20- PROJECT BUDGET:

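### The plan gives no method for assigning the at-home gel with PF (30 subjects) or without PF (10), so the between-subject PF comparison is open to selection and to clumping by enrolment block

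*Protocol*

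**What the plan says.** The 30/10 split appears in the protocol summary (section 6) and several times in section 14: at the first appointment, at the fourth appointment and under risks. At the first appointment, after the 30 subjects with PF, it reads "The remaining 10 subjects will treat the UR or UL premolar, with Opalescence 10% CP without PF". The second appointment describes handing over the gel of either kind. None of these places gives a rule for who receives which gel, and the SAP gives none either.

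The one use of random selection concerns another choice, the etched positive control in section 17: "Six randomly chosen subjects will have two strips of Block-Out Resin".

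The PF comparison is a stated aim. Section 10 puts it in the null hypothesis, and section 12 says: "With questionnaires and microhardness measurements, we will be able to determine if agents containing PF are effective and cause physical changes in enamel surfaces". The SAP compares shade change with and without PF by a rank-sum test, and analyses hardness with a fixed treatment effect, a random subject effect and Sidak-adjusted pairwise tests. Neither analysis has a term for block or source.

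Subjects are drawn from UIC, "the Universidad Autonoma de Mexico (UNAM) Graduate Program in Orthodontics, and private orthodontist dental offices in the city of Mexico" (section 14). They run "in blocks of 5 to 10 subjects at a time" (section 17). Trays are "appropriately trimmed in the UIC laboratory and/or in a private practice laboratory" (section 14).

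**The concern.** The at-home, in-office and control teeth lie in the same mouth, so those contrasts are protected by design. The PF contrast is not: it sets 10 people against 30 others. Without an assignment rule, two things can happen within the plan as written. The enroller can decide who gets which gel. Or one gel can be used up before the other is opened, so that the ten subjects without PF are a run of consecutive enrolments.

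In the second case, anything that differs between blocks, such as season, shade reader, tray laboratory or adherence to nightly wear, would look like an effect of PF. Questionnaires and hardness are at stake first, because section 12 names them as the basis for judging PF. Shade is supporting: the third-appointment text in section 14 says of the colour readings that "this is to corroborate and document that the teeth were successfully whitened".

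**Working it through.** The documents give no power, effect size, SD or sample-size calculation, so there is no design figure to reproduce. The split adds up: 30 + 10 = 40.

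**Inputs from the documents.** 30 and 10 subjects; blocks of 5 to 10. Each subject has one at-home tooth, one in-office tooth and two other premolars that serve as controls; in six subjects (three per gel) one of these two is etched. Two-sided 5%, Sidak.

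**Assumptions.** Block SD 0.2 or 0.3 of the within-block SD; within-subject correlation ρ = 0.3, 0.5 or 0.7; with-PF and without-PF are separate levels of treatment in the SAP model. With in-office and control that makes four levels and 4 × 3 / 2 = 6 pairs.

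**1. Can gel coincide with block?** Yes. 10/10 = 1 block of ten, or 10/5 = 2 blocks of five. Under simple random choice of 10 from 40 there are C(40,10) = 847,660,528 selections. The chance of filling exactly one of four blocks of ten is 4/847,660,528 = 4.7 × 10⁻⁹. For exactly two of eight blocks of five it is 28/847,660,528 = 3.3 × 10⁻⁸.

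**2. Shade, rank-sum test of 10 against 30.** No true PF effect; the ten without PF are the last ten enrolled; 40,000 simulated trials per setting; continuous readings.

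| Blocks | Block SD 0.2 | Block SD 0.3 |
|---|---|---|
| Five | 6.2% | 8.1% |
| Mixed, 5-10 | 7.0% | 9.6% |
| Ten | 8.3% | 13.2% |

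Readings rounded to coarse steps give 6.3-13.6%. With no block effect the rate is 4.5-5.0%. With gel randomised it is 4.5-4.9% in every setting.

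**3. Hardness, block effect shared by all of a subject's teeth.** The SAP's random subject effect uses the subject's other teeth to correct the at-home tooth. With k other teeth, the share of a shared shift left in the PF contrast is (1 − ρ)/(1 + (k − 1)ρ). For k = 3:

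- ρ = 0.3: 0.7/1.6 = 0.44
- ρ = 0.5: 0.5/2.0 = 0.25
- ρ = 0.7: 0.3/2.4 = 0.13

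Allowing for the six etched subjects, who have k = 2, generalised least squares gives 0.46, 0.27 and 0.14. The Sidak per-test level for six pairs is 1 − 0.95^(1/6) = 0.85%. Fitting the model by REML (20,000 simulations per setting) under the same clumping gives 0.9-1.4% after Sidak.

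**4. Hardness, block effect on the at-home tooth alone.** The other teeth carry no information about it, so the share left is 1.00. Under the same clumping the rate after Sidak is 1.8-13.8%. With gel randomised, the rate after Sidak is 0.7-1.3% across both kinds of effect.

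**5. Not computed.** The SAP specifies no questionnaire analysis, so no error rate can be given for it. Referral-source effects were not modelled, and nothing in the documents ties source to block.

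The shade rates for blocks of five and ten and the shares in steps 3 and 4 were confirmed by a second calculation. The REML rates rest on one set of simulations.

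**The case against.** Silence is not evidence of non-random assignment. The front matter and consent pages were not in the text available, and the gel may well have been randomised. That stands. A reader might infer that gel was assigned in a biased way; the documents show only that nothing prevents it.

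A reader might also infer that clumping would make gel and block inseparable for every outcome. For hardness that is wrong. Comparing at-home minus the subject's own in-office and control teeth between gels cancels any block effect common to those teeth. Under the same worst-case clumping, with one in-office and one control tooth per subject, that comparison had a false-positive rate of 4.8-5.3% at the 5% level. The SAP's own model already removes most of such an effect.

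The larger hardness figures need stacked assumptions. The 13.8% requires all of the following: the last ten enrolled get no PF, they form a single block of ten, the block SD is 0.3, the correlation is 0.7, and the effect falls on the at-home tooth only. At that correlation the residual SD is √0.3 = 0.55, so the block effect would be 0.3/0.55 = 55% of it. No document supports these values. Section 14 gives one tray specification for both laboratories and provides two contacts during the 14 days, and section 17 adds a daily log. These make a large at-home-only effect less likely, though they do not exclude it.

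The shade inflation also needs clumping. Giving every fourth subject the gel without PF would produce 4.0-4.4%. That shows a spread-out allocation would be harmless on this count, but the plan does not specify one, and a predictable sequence still lets the enroller choose.

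Finally, some differences would survive randomisation. Subjects without PF may be given potassium nitrate for sensitivity if needed (section 14, risks), which could narrow a questionnaire difference. This limits what the PF comparison can show, but is no reason to leave assignment open.

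**Conclusion.** The gap is real and limited to the PF comparisons. The plan fixes how many subjects receive each at-home gel but not how they are chosen, so the comparison in section 12 and the SAP's rank-sum test have no stated protection against selection or clumping.

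For shade, questionnaires and effects confined to the at-home tooth, complete clumping would leave gel and block inseparable. The shade illustration, about 6-13% against about 4.5% if randomised, is a worst-case allocation with an assumed block SD of 0.2-0.3. It is not an expected error rate. For hardness effects shared by a subject's teeth, 0.9-1.4% against 0.85% after Sidak is negligible, given six pairs and the two gels as separate treatment levels.

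The documents do not support extending this to the main objective. The at-home, in-office and control contrasts are made within subjects and are largely unaffected. The point merits a change to the plan, but does not undermine the main result.

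**What to change.** Add one sentence to protocol section 14: the at-home gel is assigned from a concealed random list at 30:10, held by someone who does not enrol subjects. Simple random choice of 10 of the 40 is enough. Spreading the ten over enrolment blocks, and over referral sources where practical, is optional. Sample size, the split and the SAP models stay as they are. The cost is one list to prepare and keep, and both gels in stock throughout.

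Enrolment was planned for August to December 2024 and the SAP is written in the past tense, so treatment may already be complete. In that case, report how gel was assigned and tabulate enrolment block, referral source and age by gel. If assignment was not random, label the PF comparisons exploratory. If it was random, a sentence saying so and describing the method settles the point.
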